10.6 Immunogenicity Assessments

Immunogenicity assessments are only performed in subjects from the Immunogenicity/Reactogenicity Subset to assess the immune response induced by vaccination with CVnCoV and are evaluated in 2 ways:

- Binding antibodies to the SARS-CoV-2 RBD of the S protein (IgG) measured in serum by immunoassay.
- Viral neutralizing antibodies directed against SARS-CoV-2 (MN 25 TCID50) measured in serum by a functional activity assay.

Results from the two assays are quantitative. Measures below the LLoQ are presented as half the LLoQ in the data.

Further assessments for serology status to natural SARS-CoV-2 infection (SARS-CoV-2 N protein) are performed in all subjects by immunoassay. The N protein is not a component of the CVnCoV vaccine, but is measured to determine the serostatus of subjects to the SARS-CoV-2 virus and the occurrence of SARS-CoV-2 infections during the trial (see also Section **Error! Reference source not found.**). Data provided is qualitative (positive/negative).

As the immunogenicity results would potentially unblind the subject's treatment assignment, the laboratory performing the assays keeps the results in strict confidence. The SARS-CoV-2 N protein data is not considered unblinding information.

After approval of protocol v3.0 immunogenicity assessments are no longer performed.

10.6.1 SARS-CoV-2 Serology Status

In all trial subjects, measurement of binding antibodies to the SARS-CoV-2 N protein is performed by immunoassay. Blood samples are taken on Day 1 (pre-vaccination baseline), Day 43 and Day 211 of the trial.

The (retrospective) SARS-CoV-2 serology status is defined based on levels of antibodies to the SARS-CoV-2 N protein. Subjects are defined as naïve to SARS-CoV-2 infection at baseline and Day 43, if there are no detectable SARS-CoV-2 N protein antibodies in the blood samples taken at baseline and Day 43, respectively.

Serology status at baseline is based on blood samples taken at Clinic Visit 1 (Visit Day 1) up to 2 days after 1st vaccination. The baseline definition for serology status is differing from the general baseline definition in this study (see Section 10.1).

Serology status at Visit Day 43 is based on blood samples taken at Clinic Visit 3 (Visit Day 43) 14 days after 2nd vaccination +/- 3 days.

For safety analyses, N antibody serostatus at baseline is used to define the seronegative and seropositive safety populations.

For the efficacy analyses, the subject must be seronegative/naïve to N protein at baseline and Day 43 to be considered naïve when COVID-19 cases are being counted ≥ 15 days after second trial vaccination. For endpoints where cases are counted at any time after the 1st trial vaccination, these subjects only have to be seronegative/naïve at baseline.

The same definition as given above is applied to assess the SARS-CoV-2 serology status of subjects at any other timepoint where a respective blood sample was taken; to measure infections with SARS-CoV-2 during the course of the trial.

Nota bene: Although the N antibody serostatus is to be considered an immunogenicity assessment, these values are not censored due to AV receipt.

10.6.2 Seroconversion

Seroconversion is defined by a relevant increase in antibody titer compared to baseline. The titer is the highest dilution factor that still yields a positive reading for the antibodies, i.e. larger titers correspond to larger concentration of antibodies. Depending on the type of antibodies and previous exposure of a subject to SARS-CoV-2 (as measured by antibodies to the SARS-CoV-2 N protein), different definitions of seroconversion apply:

10.6.2.1 SARS-CoV-2 RBD of S Protein Antibodies

In subjects who tested seronegative to the N protein for SARS-CoV-2 at baseline (see Section 10.6.1), seroconversion is defined as a fold increase above 1 in antibody titer against SARS-CoV-2 RBD of S protein.

In subjects who tested seropositive to the N protein for SARS-CoV-2 at baseline (see Section 10.6.1), the definition for seroconversion is a fold increase above 2 in antibody titer against SARS-CoV-2 RBD of S protein versus baseline.

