### **10.2.3 Per Protocol Immunogenicity Subset**

The PPI will include 250 subjects who belong to the Immunogenicity/Reactogenicity Subset (200 verum subjects, i.e. 100 per lot and 50 placebo subjects) and who:

- Received both doses as randomized and within the windows defined in the protocol.
- Have no major protocol deviations expecting to impact the immunogenicity outcomes as specified in the SAP.
- Have not received medical treatments (such as blood products, immunoglobulin therapy) that may interfere with 1 or both of the proposed immunogenicity measurements.
- Have a blood sample collected at 14 days (Day 43) post-second vaccination available for analysis.

The PPI will be the primary analysis population for SARS-CoV-2 RBD of S protein antibody responses and SARS-CoV-2 viral neutralizing antibody.

For assessment of seroconversion rates, the analyses will be restricted to PPI subjects who are naïve at baseline to SARS-CoV-2 RBD of S protein antibody or to SARS-CoV-2 viral neutralizing antibody depending on the endpoint analyzed.

The lot-to-lot consistency analysis on SARS-CoV-2 RBD of S protein antibody titers will be done on the PPI subjects who received 2 doses of CVnCoV vaccine coming from the same lot and who have a negative SARS-CoV-2 RBD of S protein antibody titer at baseline.

Subjects to be excluded from the PPI will be identified and reviewed at the Blinded Data Review Meeting held before unblinding of the trial. Major protocol deviations will be listed and summarized.

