**Table 6 Primary and Supportive Populations for the Analysis of Each Endpoint**

Endpoints	Primary Population	Supportive Population
Primary Safety Endpoints:		
• Solicited AEs	SASsol	-
• Unsolicited AEs	SAS 2	-
• SAEs, AESI, medically-attended AEs, AE leading to vaccine withdrawal	SAS	-
Primary Immunogenicity Endpoints:		
• SARS-CoV-2 RBD of S protein antibody titers	PPI	-
• Seroconversion to SARS-CoV-2 S protein antibody responses	PPI (RBD of S protein antibodies naïve subjects)	-
Secondary Efficacy Endpoints:		
• Any severity COVID-19	EAS	SAS
• Severity of COVID-19	EAS	SAS
• BoD scores	EAS	-
Secondary Immunogenicity Endpoints:		

• SARS-CoV-2 viral neutralizing antibody	PPI	-
• Seroconversion to SARS-CoV-2 viral neutralizing antibody	PPI (neutralizing antibodies naïve subjects)	-
• Lot-to-lot consistency on SARS-CoV-2 RBD of S protein antibody titers	PPI (CVnCoV subjects)	-
Exploratory Efficacy Endpoint:		
• Second episode of COVID-19	EAS	SAS

EAS: Efficacy Analysis Set; PPI: Per Protocol Immunogenicity set; SAS: Safety Analysis Set; SAS 2: Safety Analysis Subset; SASsol: SAS 2 for solicited adverse events analysis.

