### **10.3.6 Immunogenicity Analysis**

No formal hypothesis on immunogenicity will be tested. Descriptive statistics for the immunogenicity endpoints will be provided for a subset of subjects for each CVnCoV lot separately (n = 100 per lot), for pooled lots and for a subset of subjects in the placebo group (n = 50) on Days 1, 29 and 43.

The following analyses will be done for SARS-CoV-2 RBD of the S protein antibody concentrations and for neutralizing antibodies titers :

- Geometric mean concentrations (GMC) / geometric mean titers (GMT) by group will be summarized with their 95% CI at blood sampling time points Day 1, Day 29 and Day 43 for 250 evaluable subjects and then separately in subjects seronegative at baseline and in subjects seropositive at baseline.
- The fold change from baseline will be computed for seropositive subjects at baseline and GMFC by group will be displayed with their 95% CI at the Day 29 and Day 43 blood sampling time point.
- The number and percentage of subjects SARS-CoV-2 seronegative at baseline for whom a seroconversion is observed will be summarized and presented at each blood

sampling time point after baseline until Day 43 with exact 95% CI. Seroconversion is defined as detectable antibodies in the serum ( $\geq$  lower limit of quantification (LLOQ)).

Concentrations/titers marked as below the LLOQ will be arbitrary replaced by half of the LLOQ for GMC/GMT and GMFC computations purpose.

To assess lot-to-lot consistency, the two-sided 95% CI of the ratio of GMCs of SARS-CoV-2 RBD of S protein antibodies between subjects receiving 2 different lots of CVnCoV will be computed for Day 43.

Additional immunogenicity analyses including graphs will be described in SAP as applicable.

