# restricted to subjects naïve to SARS-CoV-2 N protein antibodies at baseline		

Table 4: Summary of Analysis Sets to be Used per Analysis - Efficacy Endpoints

Endpoint Type	Endpoint Short Description	Primary Analysis Set	Supportive Analysis Set
Secondary Efficacy Endpoint	First episodes of COVID-19 cases.	EAS	SAS#
	Severity assessment of first episodes of COVID-19 cases.	EAS	SAS#
	BoD Scores	EAS	SAS#
	Second episodes of COVID-19 cases	EAS	SAS
Exploratory Efficacy Endpoint	Second episodes of COVID-19 cases	EAS	SAS

#Including all subjects whatever their serological status at baseline and considering all events occurring at any time after the first trial vaccination.

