10.6.2.2 SARS-CoV-2 Neutralizing Antibodies

In subjects who tested seronegative to the N protein for SARS-CoV-2 at baseline (see Section 10.6.1), seroconversion is defined as a fold increase above 1 in SARS-CoV-2 neutralizing antibody titer.

In subjects who tested seropositive to the N protein for SARS-CoV-2 at baseline (see Section 10.6.1), the definition for seroconversion is a fold increase above 2 in SARS-CoV-2 neutralizing antibody titer versus baseline.

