12.7.1 Primary Immunogenicity Analyses

SARS-CoV-2 RBD of S protein antibodies (expressed as GMT) are summarized descriptively. Summaries are provided at baseline and each post-baseline sampling timepoint. The fold change (FC) from baseline is further computed and summarized for Day 29 and Day 43.

For each post-baseline timepoint, the number and percentage of subjects seroconverting with any fold increase, a 2-fold increase and a 4-fold increase are presented together with the exact 95% Pearson-Clopper CIs for the proportion of seroconverting subjects. This analysis is only done for subjects seronegative to the N protein at baseline. For a definition of seroconversion for subjects seronegative at baseline, see Section 10.6.2.

GMTs of SARS-CoV-2 RBD of S protein antibody levels over time are presented in the following figures:

- Line plot of GM FC from baseline and 95% CIs,
- Line plot of GMTs with GM and 95% CIs,
- Boxplots of GMTs with median, Q1 and Q3, and whiskers representing minimum and maximum by vaccine group.

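### The SAP's seroconversion analyses select subjects by N-protein status and count any rise, not the protocol's same-assay-naive subjects reaching LLOQ, and SAP 6.1 does not declare the change

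*SAP*

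**What the plan says.** **Protocol.** On population, section 10.2.3 states that for seroconversion rates "the analyses will be restricted to PPI subjects who are naïve at baseline to SARS-CoV-2 RBD of S protein antibody", or naive to neutralizing antibody when that is the endpoint. Table 6 repeats this for each assay separately; the RBD row reads "PPI (RBD of S protein antibodies naïve subjects". On the rule, section 10.3.6 says "Seroconversion is defined as detectable antibodies in the serum" and sets the threshold at or above LLOQ. Section 10.3.6 and the synopsis describe the population more loosely, as SARS-CoV-2 seronegative at baseline.

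**SAP.** Section 10.6.2 sorts subjects by baseline N-protein status. For N-seronegative subjects, 10.6.2.1 has "seroconversion is defined as a fold increase above 1 in antibody titer against SARS-CoV-2 RBD of S protein" and 10.6.2.2 has "seroconversion is defined as a fold increase above 1 in SARS-CoV-2 neutralizing antibody titer". For N-seropositive subjects, 10.6.2.1 says "the definition for seroconversion is a fold increase above 2 in antibody titer against SARS-CoV-2 RBD of S protein versus baseline", with a matching rule in 10.6.2.2. Section 12.7.1 then limits the analysis: "This analysis is only done for subjects seronegative to the N protein at baseline". Section 12.7.2 repeats it for neutralizing antibodies, and the footnote to Table 3 (section 9.5.7) reads "restricted to subjects naïve to SARS-CoV-2 N protein antibodies at baseline".

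SAP 9.1.2, 9.2.2 and the estimand table in 9.4 keep the protocol's term, detectable. Section 9.1.2 refers to 10.6.1 for serostatus, which is N-based.

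**The concern.** Absence of N antibody shows no serological sign of past infection. It does not show that a subject lacked RBD or neutralizing antibody at Day 1, and lacking it is what makes a later detectable value a seroconversion. Under the SAP, a subject who already had antibody stays in the denominator and is counted after any upward movement, including assay noise.

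RBD seroconversion is a primary immunogenicity endpoint, and the same rule drives a secondary one. At stake are the reported rates, mainly in placebo, where the true rate should be close to zero, and the ability to trace them to the protocol. SAP 6.1 does not help: item 5 covers analysis sets only for unblinding and authorized vaccine, and item 15 concerns N-protein seroconversion, a different endpoint. The SAP also conflicts with itself, since its endpoint sections require detectable antibody and its derivation requires a fold rise above 1.

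**Working it through.** The documents state no expected seroconversion rate or power, so there is no figure to reproduce. The check compares the rules, then sizes the difference under stated assumptions.

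**Inputs from the documents.** Values below LLOQ are set to half LLOQ (SAP 10.3, 10.6). The PPI has 100 subjects per CVnCoV lot and 50 placebo (SAP 9.5.4). SAP 12.7.1 reports any-fold, 2-fold and 4-fold rises with exact 95% CIs.

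**Step 1: where the rules agree.** Take a Day 1 value below LLOQ, carried as 0.5 × LLOQ.
- Later value below LLOQ: fold = 0.5/0.5 = 1. Not counted by either rule.
- Later value at LLOQ: fold = 1/0.5 = 2. Counted by both.

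**Step 2: where they differ.**

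| Day 1 N status | Day 1 result in the assay | Protocol | SAP |
|---|---|---|---|
| Negative | Below LLOQ | Included | Included, same result |
| Negative | At or above LLOQ | Excluded | Included, any rise counts |
| Positive | Below LLOQ | Included | Excluded |
| Positive | At or above LLOQ | Excluded | Excluded |

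No described analysis uses the above-2-fold rule for N-positive subjects, because 12.7.1 leaves those subjects out.

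**Step 3: chance that a stable, already positive placebo subject counts at one visit.** Assay error is assumed; the documents give none.
- *Two-fold dilution readout.* Reading = floor(log2 level + error), levels uniform, two independent readings, 2,000,000 draws. For error SD 0.2, 0.3, 0.4 and 0.5 log2, P(rise of at least one step) = 0.113, 0.168, 0.217 and 0.257. P(at least two steps, i.e. 4-fold) = 0.000, 0.001, 0.009 and 0.025. A separate run with SD 0.3 to 1.0 gave 0.167 to 0.364 for one step.
- *Continuous readout.* With an SD of 0.2 on the natural-log scale per reading, the difference has SD 0.2 × √2 = 0.283. P(fold > 1) = Φ(ln(1 − decline)/0.283) = 0.500, 0.355 and 0.215 for declines of 0, 10 and 20%. P(fold ≥ 2) with no decline = 1 − Φ(0.693/0.283) = 0.007.

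**Step 4: placebo, n = 50.** Expected false seroconverters per visit = number of N-negative/assay-positive subjects × chance per subject, using 0.11 to 0.50.
- 0 subjects: 0
- 1 subject: 0.11 to 0.50
- 5 subjects: 0.55 to 2.5, i.e. 1.1 to 5 percentage points

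The protocol rule counts none of them. With one such subject, the result can move from 0/49 (exact 95% CI 0 to 7.3%) to 1/50 (0.05 to 10.6%).

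**Step 5: CVnCoV, n = 200.** Assume a 90% rate in naive subjects and 4 discordant subjects who all rise: (0.90 × 196 + 4)/200 = 180.4/200 = 90.2%, against 90.0%.

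**The case against.** Several points on the other side are sound.

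- The fold-above-1 wording changes nothing for anyone below LLOQ at baseline. Only the choice of population can alter a result.
- Protocol 10.3.6 and the synopsis speak only of SARS-CoV-2 seronegative subjects, and the protocol uses the N protein to determine serostatus to the virus. Protocol 10.3.1 also leaves definitions of analysis variables to the SAP. Even so, 10.2.3 and Table 6 name the assay for each endpoint and settle the reading. Leaving details to the SAP does not cover an undeclared departure from them.
- The number affected may be zero. Exclusion criterion 1 bars positive serology, although protocol section 6 says subjects from outside COVID19-5-P-002 are not screened. Appendix 5 to the SAP, held separately, might also remove such subjects from the PPI.
- Some safeguards are planned. Baseline minimum and maximum would reveal an already positive subject. The 4-fold row removes nearly all the noise (at most 2.5% on the dilution scale). The 2-fold row does so on a continuous readout (0.7%), but on a two-fold dilution scale one step already meets it. None of this restores the protocol's denominator.
- The change log shows no edit to 10.6.2.1 or 10.6.2.2, so the rule appears to predate unblinding, while SAP 4.0 was written by an unblinded team. A derivation changed at that stage needs explaining. Returning to the definition already in the protocol is not, however, a data-driven choice.

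**Conclusion.** The concern holds. Both the population and the rule differ from the protocol, SAP 6.1 does not declare it, and the SAP is inconsistent between its endpoint and derivation sections. Followed as written, it can report a subject who already had antibody as seroconverting on a primary immunogenicity endpoint.

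The text mismatch is certain; its numerical effect is not. With 0 to 5 N-negative/assay-positive subjects among 50 placebo, the placebo rate rises by 0 to 5 percentage points per visit. The top of that range needs five such subjects and a continuous readout without waning. The CVnCoV rate moves by about 0.2 points in the illustration. The discordant counts, assay error and decline are all assumptions, and the effect of dropping N-positive, assay-naive subjects was not sized. The analysis is descriptive, so no test or decision rule is affected. The correction should be made.

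**What to change.** 1. In SAP 10.6.2.1, 10.6.2.2, 12.7.1, 12.7.2 and the Table 3 footnote, assess seroconversion in PPI subjects below LLOQ at Day 1 in the same assay, and count a post-baseline value at or above LLOQ. Keep the planned exact 95% CI. This also brings the derivation into line with 9.1.2, 9.2.2 and 9.4.
2. Keep the 2-fold, 4-fold and fold-change summaries, and report subjects already positive in that assay separately. Keep N serostatus as a descriptive split.
3. Delete the above-2-fold rule for N-positive subjects, or name the analysis that uses it.
4. Cross-tabulate Day 1 N status against Day 1 RBD and neutralizing status by group, so that the number affected is visible.
5. If the N-based version is retained, list and justify it in SAP 6.1 and show the protocol-defined rate beside it.

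The cost is SAP wording, one baseline filter and one cross-tabulation. Day 1 samples for all three assays are already scheduled, so no new data are needed. Because SAP 4.0 was prepared unblinded, the change log should say that the edit restores the protocol definition.

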10.6.2.2 SARS-CoV-2 Neutralizing Antibodies

In subjects who tested seronegative to the N protein for SARS-CoV-2 at baseline (see Section 10.6.1), seroconversion is defined as a fold increase above 1 in SARS-CoV-2 neutralizing antibody titer.

In subjects who tested seropositive to the N protein for SARS-CoV-2 at baseline (see Section 10.6.1), the definition for seroconversion is a fold increase above 2 in SARS-CoV-2 neutralizing antibody titer versus baseline.

10.7 COVID-19 Cases

COVID-19 case detection begins with the identification of subjects reporting at least one symptom from a standardized list of symptoms. Based on a scripted phone interview with trial staff, subjects suspected of having COVID-19 undergo testing for SARS-CoV-2 virus. Details of the tests performed and, in case of confirmed COVID-19 cases, details on the COVID-19 cases are recorded on the CRF.

10.7.1 Case Detection

10.7.1.1 Routine Surveillance

During all clinic visits and phone calls, subjects are reminded to contact the trial site if they have any of the following symptoms [1]:

- Fever or Chills
- Shortness of breath or difficulty breathing
- New loss of smell or taste
- Cough
- Fatigue
- Muscle or body aches
- Headache
- Sore throat
- Congestion or runny nose
- Nausea or vomiting
- Diarrhea

In addition, subjects are messaged up to twice a week to provide a yes or no response to having COVID-19 symptoms.

Those who report symptoms either at the clinic visit or by phone call, or respond “yes” to having symptoms by messaging are contacted by trial staff for a follow-up interview(s) to determine the probability of the subject having COVID-19. If the subject is suspected of having COVID-19 illness, he/she undergoes testing for SARS-CoV-2 infection, consisting of a molecular-based RT-PCR test performed at a designated local laboratory.

The result of the local RT-PCR test is recorded on the CRF as positive or negative.

10.7.1.2 Non-Routine Surveillance for COVID-19 (Positive Test Outside of Trial Site)

Subjects are reminded to contact the trial site immediately if he/she has a positive SARS-CoV-2 test performed outside of the trial site, whether or not they were symptomatic (COVID-19 illness) or asymptomatic at the time of the test.

The subject should be retested as soon as feasible to confirm the result. The RT-PCR test result is considered definitive as a virologically-confirmed case of COVID-19. If the subject is not virologically-confirmed by RT-PCR testing, he/she returns to routine surveillance for COVID-19 as a subject who is naïve to SARS-CoV-2 infection (unless determined otherwise by a seropositive test to the N protein).

If the subject was symptomatic, trial staff uses the scripted interview to collect information about the subject’s COVID-19 symptoms and medical condition.

10.7.2 Definition of Virologically-Confirmed COVID-19 Case and Onset Date

A virologically-confirmed case of COVID-19 is defined as a positive SARS-CoV-2 specific RT-PCR test performed at the designated local laboratory in a person with clinically symptomatic disease consisting of one or more of the symptoms listed in Section 10.7.1.

The onset date of a virologically confirmed COVID-19 case (identified during routine surveillance or outside of the trial) is defined as the date of symptom onset as recorded on the CRF. If the date of symptom onset is partially or completely missing, the following imputation rules are applied:

1. If the date is present but incomplete and it can be confirmed, based on the available date parts, that the onset was before first vaccination, then the missing date parts are imputed as the earliest possible date.
2. If a present but incomplete date is still incomplete after checking point 1, and it can be confirmed, based on the available date parts, that the onset was before 15 days after second vaccination, the missing date parts are imputed with the earliest possible date on or after first vaccination.
3. If a present but incomplete date is still incomplete after checking points 1 and 2, it is imputed with the earliest possible date ≥ 15 days after second vaccination.
4. If the symptom onset date is completely missing, the date of first positive RT-PCR test is used instead.
 - a) If the first positive RT-PCR test is incomplete then points 1-3 above should be applied on the first positive RT-PCR test date.

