9.5.5 Efficacy Analysis Set (EAS)

The EAS includes all subjects of the SAS who:

- Received both trial doses according to their randomization (two doses of the same lot of CVnCoV if randomized to that lot or two doses of placebo if randomized to placebo).
- Had not developed a virologically-confirmed case of COVID-19 before trial entry (based on exclusion criteria 1, see Trial Protocol)
- Had not developed a virologically-confirmed case of COVID-19 (definition in Section 10.7.2) or an asymptomatic case of SARS-CoV-2 (definition in Section 10.8) before 15 days after the second vaccination.
- Had not stopped the trial before 15 days after the second vaccination.
- Were SARS-CoV-2 naïve at baseline (Visit Day 1) and Visit Day 43 (based on seronegativity to N protein in the blood sample).
- Were not unblinded or in receipt of AV prior to 15 days after the second vaccination (See Section 10.10)

Where available the information assessed by the independent adjudication Committee of clinicians (Section 10.7.5) is used.

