10.7.4 COVID-19 Case Definition for Efficacy Analysis

A case of COVID-19 meeting the case definition for efficacy analysis is defined as follows:

- Virologically-confirmed case of COVID-19 (of any severity) defined as a positive SARS-CoV-2 specific RT-PCR test in a person with clinically symptomatic COVID 19, see Section 10.7.2.
- Symptom onset ≥ 15 days after second trial vaccination, i.e.

$$\text{Start date of symptoms} - \text{date of second vaccination} \geq 15 \text{ days.}$$

See Section 10.7.2 for further details on definition of symptom onset.

- First episode of virologically-confirmed COVID-19, i.e. the subject must not have a history of virologically-confirmed COVID-19 illness at enrollment or have developed a case of virologically-confirmed COVID-19 before 15 days after the second trial vaccination.
- Subject is SARS-CoV-2 naïve at baseline and Day 43 (defined as seronegative to N protein in the blood samples collected at baseline and Day 43). See Section 10.6.1 for further details.

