10.7.5 Adjudication of COVID-19 Cases

An independent Committee of clinicians is formed to adjudicate some COVID-19 cases, and asymptomatic cases of SARS-CoV-2 infections (Section 10.8). The Committee is blinded to the treatment assignment of the subject. The cases are adjudicated by the members with respect to the following questions:

- Is the case a virologically-confirmed case of COVID-19 defined as a positive SARS-CoV-2 specific RT-PCR test in a person with clinically symptomatic COVID-19 with one or more of the symptoms listed in Section 10.7.1?
- Was the RT-PCR test performed at the CureVac designated central laboratory?
- Was the symptom onset of the case ≥ 15 days following the second vaccination? Or did it occur before 15 days following the second trial vaccination?
- Was the subject naïve or non-naïve to SARS-CoV-2 at baseline and Day 43? (defined as being seronegative or seropositive to the SARS-CoV-2 N protein at baseline and Day 43).
- Was the subject 18 to 60 years of age or ≥ 61 years of age?
- Was the subject asymptomatic? If asymptomatic, was the RT-PCR test positive ≥ 15 days following the second vaccination or before?
- Was it a mild, moderate, or severe case of COVID-19 based on the provided clinical definitions?
- Did the subject require supplemental oxygenation? What type of oxygen support did the subject receive?
- Was the subject hospitalized? Was the subject admitted to the ICU?
- Did the subject die? Due to COVID-19 or other cause?

NB: The Adjudication questionnaire uses the term “CureVac designated central laboratory” although in this study the local laboratory had been designated by CureVac to perform the RT-PCR test.

COVID-19 case summary data as provided by the Adjudication Committee is used for all relevant definitions and analyses, i.e. especially all efficacy cases have to be confirmed by the Adjudication Committee. Where the adjudicated data conflicts with other data recorded on the CRF (e.g. severity of the event, or baseline serology status), the adjudication data generally overrules the other data available. This applies to both COVID-19 cases and asymptomatic cases of SARS-CoV-2 infections.

Exceptions:

1. For the analysis of COVID-19 cases by age group, the age at trial entry as recorded on the CRF rather than the age at onset (as assessed by the Adjudication Committee) is used.
2. The case onset date is also taken from the CRF, irrespective from the onset date recorded on the Adjudication Form.

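### SAP 10.7.2 can impute a partial symptom-onset date into the efficacy window for a symptomatic case whose positive RT-PCR test came before the window

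*SAP*

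**What the plan says.** SAP 10.7.2 takes the onset of a confirmed case as the symptom-onset date on the CRF. If that date is incomplete, four rules apply in order.

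- Rule 1 covers dates whose recorded parts show onset before dose 1.
- Rule 2 applies where "it can be confirmed, based on the available date parts, that the onset was before 15 days after second vaccination".
- Rule 3 takes everything left over: "If a present but incomplete date is still incomplete after checking points 1 and 2, it is imputed with the earliest possible date" that is at least 15 days after dose 2. It sets no upper limit.
- Rule 4 is the only one that refers to the test: "If the symptom onset date is completely missing, the date of first positive RT-PCR test is used instead".

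The resulting date is used downstream. For the 15-day criterion, SAP 10.7.4 says "See Section 10.7.2 for further details on definition of symptom onset". Table 8 in SAP 10.11 counts events by onset on or after dose 2 + 15 days. The EAS in SAP 9.5.5 keeps only subjects who "Had not developed a virologically-confirmed case of COVID-19 (definition in Section 10.7.2) or an asymptomatic case of SARS-CoV-2" infection before that day.

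**The concern.** For a subject who already had symptoms when swabbed, the positive test is an upper bound on onset. Rule 3 ignores that bound, so it can produce an onset date after the test that confirmed the case. Rule 4 shows that the SAP accepts the test date as evidence of timing. A subject with the month recorded can therefore be classified less accurately than one with no onset date at all.

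The 15-day boundary does two jobs. It decides which cases enter the VE numerator, and it decides which subjects leave the EAS because they were infected early. A misplaced date gets both wrong: a case from before the period of full protection is counted, and a subject who should have been excluded is kept.

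**Working it through.** No sample size, power or case count in the plan depends on this rule, so there is no stated figure to reproduce. The check applies the rules literally, looks for another provision that would catch the error, and then sizes one misplaced case.

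**1. One case through the rules (invented dates).** Dose 1 on 10 Feb 2021, dose 2 on 10 Mar 2021, window start 10 Mar + 15 days = 25 Mar. Onset is recorded as March 2021 with the day missing. The subject was symptomatic and first RT-PCR positive on 18 Mar, 8 days after dose 2.

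- Rule 1: the latest compatible date, 31 Mar, is not before 10 Feb. Not met.
- Rule 2: 31 Mar is not before 25 Mar. Not met.
- Rule 3: onset is set to 25 Mar, which is 7 days after the positive test. Then 25 Mar − 10 Mar = 15, the criterion is met, and the case counts with 1 day of follow-up.
- Had onset been wholly missing, rule 4 would give 18 Mar. The case would not count and the subject would leave the EAS.

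**2. Would anything else catch it?**

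- The case definition also bars subjects who "have developed a case of virologically-confirmed COVID-19 before 15 days after the second trial vaccination", but the only date the SAP defines for a symptomatic case is its onset date. The EAS exclusion refers back to SAP 10.7.2. SAP 10.8 uses the test date as onset only for asymptomatic infections.
- Adjudication: SAP 10.7.5 asks the committee about the 15-day boundary but adds "The case onset date is also taken from the CRF, irrespective from the onset date recorded on the Adjudication Form".
- Day 43 serology: "Serology status at Visit Day 43 is based on blood samples taken at Clinic Visit 3 (Visit Day 43) 14 days after 2nd vaccination", within 3 days either side. Here that is 21 to 27 Mar, or 3 to 9 days after the positive test. It measures antibody, not the date of the test.

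**3. How often rule 3 misplaces an eligible date.** Assume dose-2 dates spread evenly over 2021, true onset 0 to 14 days after dose 2, and only the day missing. Rule 3 moves 4035 of 5475 combinations (73.7%) into the window. With only the year recorded it moves 97.8%. These shares are conditional on having a partial date and an early onset; they are not prevalences.

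The test date would expose those moved cases whose test also fell before the window:

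| Assumed lag, onset to test | Moved cases tested before the window | Share of 4035 |
|---|---|---|
| 0 days | 4035 | 100% |
| 2 days | 3341 | 83% |
| 5 days | 2390 | 59% |

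**4. Weight of one misplaced case.** SAP 12.8.1.1 gives VE = 1 − [p/(1−p)]/r, which equals 1 − (CVnCoV cases / placebo cases)/r. Take r = 2, from 1:1:1 allocation with equal follow-up per subject (assumed). The case counts are also assumed.

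| Cases, CVnCoV : placebo | VE as counted | Remove one CVnCoV case | Remove one placebo case |
|---|---|---|---|
| 5 : 5 | 50% | 1 − (4/5)/2 = 60.0% | 1 − (5/4)/2 = 37.5% |
| 10 : 10 | 50% | 1 − (9/10)/2 = 55.0% | 1 − (10/9)/2 = 44.4% |
| 20 : 20 | 50% | 1 − (19/20)/2 = 52.5% | 1 − (20/19)/2 = 47.4% |

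Two extra cases in each arm, 22 : 22, leave VE at 50%.

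**The case against.** Four objections deserve weight.

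**Symptoms can follow a positive test.** SAP 10.8 and Protocol 9.2.2 provide for subjects who test positive without symptoms, are watched for at least 2 weeks, and become COVID-19 cases if symptoms develop. Protocol 9.2.2 names routine screening of health care staff as one reason for such tests. A reader might infer that onset can never be later than the first positive test and that every imputed date should be capped there. The documents do not support that. A subject positive on day 12 after dose 2 with symptoms on day 16 meets the onset criterion, and an unconditional cap would misclassify that case if its onset date were partial. This objection stands and limits the fix.

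**There are safeguards.** Subjects must be N-seronegative at Day 43, and SAP 10.7.5 says efficacy cases have to be confirmed by the committee. Keeping the CRF onset date does not plainly void the committee's answer on whether a case qualifies. This stands in part: the safeguards may remove some misplaced cases. They are not dependable, because the documents give no assay sensitivity, the same SAP section says that only some cases are adjudicated, and Protocol 9.2.1.4 makes adjudication optional.

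**It should be rare.** Symptoms are prompted up to twice a week and taken in a scripted interview (Protocol 9.2.1.1.1), and missing data are queried (Protocol 11.4). This stands.

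**Nothing is decided on it.** Efficacy is secondary and described without success criteria (Protocol 10.3.7.1). This stands, and keeps the point minor.

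**Conclusion.** The gap is real but narrow. Rule 3 can date a symptomatic case after its own confirming test and count it, and no other provision reliably prevents this. It needs a partial onset date whose possible range spans dose 2 + 15 days. Dates wholly before the boundary are handled by rules 1 and 2, and months wholly after it are placed correctly.

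Two stronger readings go too far. One is that any such subject necessarily becomes an efficacy case; Day 43 serology or adjudication may still remove the subject. The other is that VE is biased in a known direction. The rule does not depend on arm: a misplaced CVnCoV case lowers VE and a misplaced placebo case raises it.

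At assumed r = 2 and 20 : 20 cases the shift is about 2.5 percentage points per case, and larger with fewer cases. Neither the case counts nor the number of partial dates is in the documents, so these figures are illustrations only. This is a worthwhile clarification of a secondary, descriptive analysis.

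**What to change.** Add to rules 1 to 3 of SAP 10.7.2:

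- For a subject who was symptomatic at the first positive RT-PCR, the imputed onset may not be later than that test date. If the test date is before dose 2 + 15 days, the case is pre-window for both the case definition (SAP 10.7.4) and the EAS exclusion (SAP 9.5.5).
- A subject recorded as asymptomatic at that test who later developed symptoms is exempt from the cap. The imputed onset is then not earlier than the test date.
- Report the number of imputed onset dates by group.

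For symptomatic subjects whose test falls on or after the boundary, rule 3 already gives a date no later than the test, provided the recorded month agrees with the test, so the cap changes nothing for them. Some early onsets with a later test will still be placed in the window; the test date cannot settle those, and the count by group shows how many cases could be affected.

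The cost is a few sentences, a small programming change and one table row. Rule 4 already uses the RT-PCR date, and SAP 10.8 already has asymptomatic infections documented on the CRF. SAP 6.0 states that version 4.0 was written by an unblinded team, which is a further reason to settle boundary dates by a written rule that ignores arm.
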